5.13 Clinical Safety Laboratory Tests

The list of clinical safety labs and the definitions of measures of potential drug-induced liver injury (DILI) are the same as described in the M-SAP with the following additional analyses:

- Digestive enzymes: amylase, lipase
- Hormones: ACTH, cortisol, total testosterone (males only), luteinizing hormone (males only)
- Thyroid function: free T4, T3
- Cosyntropin stimulation testing: abnormal response is defined as a maximum cortisol concentration less than 18 µg/dL after intravenous (IV) cosyntropin injection.

5.14 Menstrual Cycle Questionnaire

A menstrual cycle questionnaire will be completed by women of childbearing potential during each clinic visit. The menstrual cycle questionnaire will capture the days of menstruation and information about the quality of menstrual flow and will be assessed by a qualified healthcare provider. Additional information about assessment of the menstrual cycle questionnaire is detailed in the RGF Manual of Procedures.

6. Statistical Methodology

6.1 Analysis Sets

The following analysis sets will be used for testing efficacy, pharmacokinetics, and safety endpoints:

- Efficacy Full Analysis Set (FAS): Participants who were randomized within RGF plus
 placebo participants from Regimens A, B, C, D, E, G, classified according to their
 randomized treatment assignment. Observations made after premature permanent
 discontinuation of study drug are included in this sample, should such participants remain on
 study. Observations completed after regimen data lock will be excluded. Participants
 determined to not meet ALS diagnostic criteria are excluded.
- Efficacy Concurrent-controls (ECC) Set: The subset of participants in the FAS analysis set
 who were randomized within RGF or randomized to placebo within RGG at or prior to the
 date when the last RGF participant was randomized, exclusive of RGG participants who were
 also randomized within RGF. This is the primary analysis set for primary and secondary
 analyses.
- Efficacy Regimen-only (ERO) Set: The subset of participants in the FAS analysis set who
 were randomized within RGF.
- Efficacy Common Mode of Administration (ECM) Set: The subset of participants in the FAS
 analysis set from Regimens B, C, D, F, G, and any other regimens in which study drug is
 administered orally.
- Efficacy Per-protocol (EPP) Set: The subset of participants in the ECC analysis set who initiated study treatment and who meet other requirements for protocol compliance as specified in the R-SAP, including compliance taking study drug (defined in Section 5.12), classified according to the treatment they actually received. If a participant's data are truncated for inclusion in the EPP analysis set due to a time-dependent event (e.g., non-adherence to protocol-specified dosing, initiation of a prohibited medication, initiation of a medication approved for treatment of ALS), clinical events observed after the censoring event will be excluded from the EPP analysis set. Data from placebo participants shared from other regimens will not be truncated due to non-adherence to protocol-specified dosing. Final specification of participants included vs. excluded from the EPP analysis set will be defined prior to data lock.
- Pharmacokinetic Analysis (PKA) Set: Participants who received at least one dose of active ABBV-CLS-7262 within RGF and from whom at least one PK sample was collected.

- Safety Full (STF) Set: Participants who received at least one dose of study drug within RGF plus placebo participants from Regimens A, B, C, D, E, G who had an opportunity to complete placebo-controlled follow-up, who are not known to be ineligible for RGF, and who received at least one dose of study drug in their respective regimen, classified according to the treatment they actually received. Observations made after premature permanent discontinuation of study drug are included in this sample, should such participants remain on study. Observations completed after regimen data lock are excluded.
- Safety Concurrent Control set (SCC): The subset of participants in the STF analysis set who
 were randomized within RGF or randomized to placebo within RGG at or prior to the date
 when the last RGF participant was randomized, exclusive of RGG participants who were also
 randomized within RGF.
- Safety Narrow (STN) Set: The subset of participants in the STF analysis set who were exposed to interventions administered orally.
- Safety Regimen-only (SRO) Set: The subset of participants in the STF analysis set who were randomized within RGF.

The meaning of regimen data lock and the criteria for inclusion of data for placebo participants assigned to other regimens at the time of regimen data lock will be defined in the HEALEY ALS Platform Trial Data Management Plan and the HEALEY ALS Platform Trial Data Sharing Plan. Specifically, concurrent placebo participants from RGG randomized at or prior to the date when the last RGF participant was randomized will be included for RGF analysis.

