4.4 Active Treatment Extension Eligibility

Participants who complete the 24-week placebo-controlled period will participate in the ATE unless consent is withdrawn. Participants in the 120 mg and 240 mg active treatment groups will continue to receive the same assigned dose for the ATE period. Participants in the placebo group will be assigned to active treatment with 120 mg ABBV-CLS-7262 for the ATE period. The ATE will remain blinded to dose level and original placebo-controlled treatment assignment for sites, investigators, and participants.

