2.0 Overview of Primary Analysis and Design

2.1 Primary Analysis

The primary analysis population includes the subset of participants in the Full Analysis Set who were randomized within Regimen F or randomized to placebo within Regimen G, exclusive of Regimen G participants who previously randomized within Regimen F (Efficacy Concurrent Controls analysis set).

The primary analysis is a Bayesian shared parameter analysis of mortality and function (ALSFRS-R) and is described in the ALS Master Protocol Recommended Statistical Analysis, Design and Simulation Report Section 2.0 Dated February 6, 2023 (Appendix I of the HEALEY ALS Platform Trial Master Statistical Analysis Plan v3.0). For Regimen F, the model will be modified to include independent treatment effects for each dosage of ABBV-CLS-7262.

The treatment effect for T=0,1,2 (control, anchor, and high dose respectively) is parameterized as the disease rate ratio (DRR): $\exp(\theta_T)$. For a placebo patient, the DRR is set equal to 1 (θ_0 = 0). The prior distribution for the DRR for the anchor dose and high dose in Regimen ABBV-CLS-7262, T=1,2, is uniform between 0 and 2, placing equal weight on a DRR<1 and DRR>1:

$$\exp(\theta_T) \sim Unif(0,2), T = 1,2.$$

The primary analysis will compare the anchor dose to control. The comparison of the high dose to control will be a secondary analysis.

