2.4 Goodness of Fit Diagnostics and Sensitivity Analyses of Primary Efficacy Analysis

The goodness-of-fit diagnostics, supportive analyses, and sensitivity analyses will be performed for the primary efficacy analysis and will be conducted on the primary analysis population unless otherwise specified. Analyses will follow those specified in Section 4.0 of the ALS Master Protocol Recommended Statistical Analysis, Design and Simulation Report Dated February 6, 2023 (Appendix I of the HEALEY ALS Platform Trial Master Statistical Analysis Plan v3.0) with the following modifications:

 Concurrent shared control population will serve as the primary analysis population and a sensitivity analysis with all shared controls from Regimens A-G will be conducted.

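### Regimen G placebo participants who were also randomized in Regimen F are removed from ECC and SCC only; FAS and ECM, and possibly STF and STN, can still hold them as controls

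*SAP*

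**What the plan says.** SAP 6.1 defines two parent sets that borrow placebo participants from other regimens.

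- **FAS:** everyone randomized in RGF plus "placebo participants from Regimens A, B, C, D, E, G, classified according to their" randomized arm.
- **STF:** everyone dosed in RGF "plus placebo participants from Regimens A, B, C, D, E, G who had an opportunity to complete placebo-controlled follow-up", provided they are not known to fail RGF eligibility and took at least one dose in their own regimen.

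The exclusion of repeat enrollees appears one level down. ECC, a subset of FAS, admits RGG placebo participants randomized up to the "date when the last RGF participant was randomized, exclusive of RGG participants who were" also in RGF. SCC has the same exclusion within STF. EPP inherits it, being "The subset of participants in the ECC analysis set who initiated study treatment" and met further compliance requirements. Appendix 1 (Sections 1.0, 2.1 and 2.3) applies it to the primary and interim population in slightly different words: "exclusive of Regimen G participants who previously randomized within Regimen F".

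The oral-route subsets do not carry it. ECM is the part of the full "analysis set from Regimens B, C, D, F, G, and any other regimens in which study drug is" taken by mouth, and STN is the equivalent part of STF. Appendix 1, Section 2.4 adds that "a sensitivity analysis with all shared controls from Regimens A-G will be conducted" for the primary model.

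On exposure, RSA 4.4 states: "Participants in the placebo group will be assigned to active treatment with 120 mg ABBV-CLS-7262 for the ATE period".

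**The concern.** The plan expects some people to be randomized in RGF and later in RGG, and it protects the primary analysis set against them. The parent sets have no such protection. A person who left RGF and was then randomized to RGG placebo qualifies for FAS on both counts: as an RGF participant, and as an RGG placebo control.

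Two things would be at stake.

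- **Independence.** One person could contribute to both sides of the contrast. The repeated-measures model in SAP 6.5.2 gives each participant one regimen effect and one treatment indicator, with nothing linking two enrollments. STF classifies people by treatment actually received, which has two answers for someone given active drug in RGF and placebo in RGG.
- **Contaminated controls.** The RGG placebo record would probably belong to someone who has already taken the study drug.

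The analyses concerned are meant to show that the result is robust to the choice of shared controls, so their control group should be at least as clean as the primary one.

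**Working it through.** **1. The plan's own counts.** From SAP 2.6, the first 240 participants are allocated 2:1:1 and the final 60 are allocated 3:1 (120 mg to placebo).

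- 120 mg: 240 × 2/4 + 60 × 3/4 = 120 + 45 = 165
- 240 mg: 240 × 1/4 = 60
- Placebo: 240 × 1/4 + 60 × 1/4 = 60 + 15 = 75

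Adding the 60 RGG controls assumed in Appendix 1, Section 3.1 gives 75 + 60 = 135 concurrent controls, which matches the stated figure. Active assignment in RGF is (165 + 60)/300 = 225/300 = 75%.

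**2. The definitions side by side.**

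| Set | Drawn from | RGF/RGG exclusion |
|---|---|---|
| FAS | RGF plus placebo from A–E and G | Not stated |
| ECC | FAS | Stated |
| EPP | ECC | Inherited |
| ECM | FAS | Not stated |
| ERO, SRO, PKA | RGF only | Not needed |
| STF | RGF plus placebo from A–E and G | Not stated; eligibility filter only |
| SCC | STF | Stated |
| STN | STF | Not stated |
| Appendix 1 primary and interim population | FAS | Stated |

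ECC is a subset of FAS. If FAS had already dropped these people, the exclusion in ECC would have nothing to do. The natural reading is that they are in FAS. FAS also lacks the RGG randomization-date limit that ECC has, so RGG placebo participants randomized after RGF closed can enter it, subject to the data-lock cut-off.

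**3. Where the affected sets are used.**

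- FAS and ECM are named as sensitivity sets for the repeated-measures model (SAP 6.5.2) and survival (6.5.4), and are also analysed by random slopes (6.5.3) and CAFS (6.5.5).
- FAS also serves the comparison of controls across regimens (6.5.8) and weight (6.6.4).
- The all-controls analysis of the primary model is in Appendix 1, Section 2.4.
- STF and STN are safety sets.

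**4. Possible size.** The documents give no count of repeat enrollees. Let m be the number of RGG placebo records that belong to former RGF participants; m = 1, 6 and 12 are assumptions.

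- People behind the 300 + 60 = 360 planned records: 360 − m = 359, 354, 348.
- Share of the 60 RGG controls: 1/60 = 1.7%, 6/60 = 10%, 12/60 = 20%.
- Share of 135 controls: 1/135 = 0.7%, 6/135 = 4.4%, 12/135 = 8.9%.

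For the effect estimate, suppose a true 30% slowing, every exposed control carrying all of it, and a simple ratio of mean progression rates with C controls:

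apparent slowing = 1 − 0.7 / [(C − 0.3m)/C]

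| C | m = 1 | m = 6 | m = 12 |
|---|---|---|---|
| 135 (concurrent only) | 29.8% | 29.1% | 28.1% |
| 285 (assumes 150 A–E controls) | 29.9% | 29.6% | 29.1% |
| 435 (assumes 300 A–E controls) | 30.0% | 29.7% | 29.4% |

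The 135 row is conservative for FAS, which adds A–E controls. The calculation covers carried-over drug effect only. It does not cover any tendency of repeat enrollees to progress more slowly, which would push the same way.

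**The case against.** The strongest reply is that SAP 6.1 leaves the criteria for including other regimens' placebo data to the Data Management Plan and the Data Sharing Plan. Those documents, the M-SAP and the Master Protocol were not available, and any of them may hold a general one-record-per-person rule. That is possible. But SAP Section 1 makes the R-SAP authoritative on shared placebos, and the R-SAP writes FAS and STF out in full. The closing sentence of 6.1 even says concurrent RGG placebo participants will be included, without repeating the exclusion. A rule elsewhere would not cure the definition.

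Three further points limit the finding and are fair.

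- STF's eligibility filter might remove repeat enrollees. The RSA exclusion criteria list neither prior exposure to ABBV-CLS-7262 nor prior platform participation, but the Master Protocol criteria also apply and could not be checked.
- The sets are defined by participant, and the model uses a participant identifier, so appearing twice is not certain. The SAP does not say how a repeat enrollee would be represented.
- ERO and EPP are also named sensitivity sets, and the key CAFS sensitivity analysis is in ECC. All of these are clean, so the check on the primary result does not rest on FAS and ECM alone.

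A reader might also infer more than the documents support:

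- *That A–E placebo participants who later joined RGF are double counted too.* No passage describes or excludes that route.
- *That every RGF completer has had active drug.* RSA 4.4 excepts withdrawal of consent, and under RSA 6.10 people who stopped study drug but stayed in follow-up may enter the extension without restarting it.
- *That repeat enrollees are survivors of at least 24 weeks.* No interval between enrollments is given, and early termination is allowed.
- *That ECM is a sensitivity set for the Bayesian primary model.* The available text names only the all-controls A–G analysis for that model.

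**Conclusion.** The gap is real on the text and should be closed before data lock. Read as written, FAS and ECM can include a former RGF participant as an RGG placebo control, probably one already exposed to the drug. STF and STN can too unless the eligibility filter removes that person. The consequences fall on supportive, sensitivity and safety analyses. ECC, EPP, SCC and the interim population are protected, so a reader should not infer any threat to the primary or secondary inference.

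The likely efficacy bias is small and towards the null: at most about 2 percentage points off a 30% slowing in the cases shown (30% to 28.1% with 12 of 135 controls). This rests on invented counts, a full carry-over of effect and a simple rate ratio rather than the Bayesian model. The case for change is less the expected size than the fact that the robustness analyses would have weaker protection than the analysis they test.

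**What to change.** - In SAP 6.1, state in both the FAS and STF definitions that the RGG placebo record of anyone also randomized in RGF is left out, so the person appears once, under the RGF assignment. ECM and STN then inherit the rule, and ECC and SCC membership does not change.
- Use one wording throughout. Section 6.1 says *also* randomized in RGF, while Appendix 1 says *previously*; these differ in scope.
- Repeat the exclusion in the closing sentence of 6.1 on concurrent RGG placebo participants.
- Run a participant-ID match across regimens before lock and report the number of matches. Extend the one-record-per-person rule to A–E placebo participants only if the match finds any who were also randomized in RGF.

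The cost is a sentence in each definition, the ID match, and the loss of a few shared-control records from the sensitivity and safety sets.

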6.2 Baseline Characterization

The specification of baseline characteristics is the same as described in the M-SAP with the addition of ALSFRS-R domain scores, ALSAQ-40 domain scores and symptom index, CNS-BFS total score, ROADS total score, quantitative voice characteristics, TRICALS score, and CSF NfL concentration.

6.3 Primary Efficacy Analysis and Supportive Analyses

The primary analysis for RGF is a Bayesian shared-parameter model of function and survival. The model will include both ABBV-CLS-7262 treatment groups and the placebo group with primary inference based on comparison of the 120 mg dosage vs. placebo in the ECC analysis set. Details of the model, including documentation of operating characteristics under a range of scenarios, are provided in the MPRDR (Appendix 1 of the M-SAP). Additional details of operating characteristics specific to RGF are provided in Appendix 1 of this R-SAP.

The estimand of the primary analysis is the relative rate of disease progression (the "disease rate ratio" or DRR) of active treatment relative to placebo in the ECC population under an assumption that active treatment slows mean time to death or death equivalent by the same proportion as treatment slows the mean rate of functional progression as measured by change in ALSFRS-R total score over time. The estimand is defined by the following attributes:

- Treatment: ABBV-CLS-7262 120 mg treatment vs. placebo.
- Population: patients diagnosed with ALS.

- Variables: time to death or death equivalent and rate of change in ALSFRS-R total score from baseline to the Week 24 Visit.
- Intercurrent event 1: treatment discontinuation due to death or death equivalent: no ALSFRS-R data from participants who reach the death or death equivalent endpoint are included in the analysis, handled via mortality component in model, composite variable strategy approach.
- Intercurrent event 2: treatment discontinuation not due to death or death equivalent: handled
 via treatment policy approach, all data will be used including data collected during the
 placebo-controlled period after treatment discontinuation regardless of concomitant
 medication, for those participants who have not been censored due to mortality. Missing data
 post-treatment will not be imputed and will be handled via missing at random assumption.
- Population-level summary: mean ratio of hazard or progression rate of active treatment relative to placebo estimated by DRR.

Supportive analyses are described in Sections 6.5.2 through 6.5.5.

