3.1 Simulation Scenarios

Trial simulations for Regimen F assume that Regimen F is the 6th regimen with a 7th regimen (Regimen G) also enrolling concurrently with a total of N=240 and 60 controls in Regimen G. Under the primary concurrent only shared control analysis there is expected to be a total of N=165 treated on the anchor 120mg dose in Regimen F and N=135 shared controls. Treatment effect assumptions will vary across the anchor dose for Regimen F and operating characteristics will be reported for this regimen/dose. The other 6 regimens will be assumed to be Null (no benefit on ALSFRS-R or mortality).

Additional simulation assumptions are:

- Accrual of 40 participants per month
- · Non-mortality dropout rate of 2% per month
- · Mortality rate of 5% over 24 weeks.
- ALSFRS-R slope distribution and measurement error for Regimen F is the same as PRO-ACT
- Rates of usage and effects of Standard of care (SOC). Effects of SOC will be multiplicative effects to the individual rates of progression applied first before any treatment effect (see below).
 - Edaravone usage at baseline is 25% with an assumed 30% slowing over natural progression for those participants who are on edaravone
 - Relyvrio usage at baseline is 60% with an assumed 25% slowing over natural progression for those participants who are on Relyvrio
 - $\circ~$ The treatment effect for those participants on both edaravone and Relyvrio is capped at 30% slowing.

Treatment effects for Regimen F will be simulated under the Null with 0% slowing in disease progression and under an alternative with 30% slowing in disease progression. The 30% slowing due to treatment in Regimen F is assumed to be an additional, additive effect on top of any effect of the standard of care (see SOC effect above). This additive effect on the slope will be specific to each SOC group (those not on edaravone or Relyvrio, those only on edaravone, those only on Relyvrio, and those on both) based on the expected control rate of progression within that subgroup to achieve a 30% slowing.

Simulations are performed without futility stopping.

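### As written, the primary analysis drops every ALSFRS-R score, including those recorded before the event, from anyone who dies or reaches a death equivalent, so its function component rests on participants who did not reach that endpoint

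*SAP*

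**What the plan says.** SAP 6.3 defines the primary estimand. Its variables are "time to death or death equivalent and rate of change in ALSFRS-R total score from baseline to the Week 24 Visit", joined in a single DRR "under an assumption that active treatment slows mean time to death or death equivalent by the same proportion" as it slows functional decline.

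For intercurrent event 1 (discontinuation due to death or death equivalent), "no ALSFRS-R data from participants who reach the death or death equivalent endpoint are included in the analysis", and the event is "handled via mortality component in model, composite variable strategy approach". For intercurrent event 2 (other discontinuation), all data are used, but only "for those participants who have not been censored due to mortality".

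The exclusion attaches to the participant. It has no qualifier limiting it to visits after the event, and the second bullet fits that reading. Nothing in the Regimen-Specific Appendix (RSA), the SAP body or SAP Appendix 1 restores the earlier scores.

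The supportive models differ. SAP 6.5.2 (repeated measures) and 6.5.3 (random slopes) use all data and treat only data missing because of death as missing at random, so scores recorded before death stay in.

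**The concern.** A composite approach to death needs no function score after the event. It does not require discarding scores recorded while the participant was alive and under follow-up. Under the rule as written, whether a participant's function data count depends on an outcome that the model itself assumes treatment changes.

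If faster progressors are more likely to die, an effective drug keeps more of them in the active arm's function data than remain in the placebo arm's. The function contrast is then pulled toward no effect. If a drug raised mortality without helping function, the survivors on active treatment would look slower, and the function component would partly offset the harm signal.

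The primary test is the gatekeeper for every secondary endpoint. As written, it would also use different ALSFRS-R data from the first-ranked secondary endpoint, the ALSFRS-R repeated-measures analysis.

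**Working it through.** **Inputs from the documents**
- SAP Appendix 1, 3.1: "Mortality rate of 5% over 24 weeks"; "N=165 treated on the anchor 120mg dose in Regimen F and N=135 shared controls"; 30% slowing, that is DRR 0.70.
- SAP Appendix 1, 2.2: one-sided 2.5%.
- SAP Appendix 1, Table 3.2.1: power 0.843 with mean estimate 0.70 (function and mortality); power 0.801 with mean estimate 0.71 (function only).

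**Step 1. Participants affected**
- Controls: 135 × 0.05 = 6.75 deaths.
- 120 mg at hazard ratio 0.70: 1 − 0.95^0.7 = 3.5%, so 165 × 0.0353 = 5.8 deaths.
- Total 12.6 under the alternative and 300 × 0.05 = 15 under the null, about 4–5% of the 165 + 135 = 300 in the contrast.

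**Step 2. Where the information lies**

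The power of 0.843 cannot be rebuilt from first principles, because neither the PRO-ACT slope figures nor the MPRDR model is in the documents. A two-component approximation on the log-DRR scale can be calibrated to one row of Table 3.2.1 and tested on the other.
- Mortality information: deaths × p(1 − p), with p = 165/300 = 0.55. This gives 12.57 × 0.2475 = 3.1.
- Total information implied by 0.843: [(1.007 + 1.960)/0.3567]² = 69.2, where 0.3567 = −ln 0.70.
- Function information: 69.2 − 3.1 = 66.1. Mortality carries 3.1/69.2 = 4.5% of the weight.
- Test on the function-only row (15 deaths, mortality information 3.7): z = 66.1 × 0.3567/√69.8 = 2.82. Predicted power is Φ(2.82 − 1.96) = 0.805 (stated 0.801). Predicted estimate is exp(−66.1 × 0.3567/69.8) = 0.713 (stated 0.71).

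Both rows therefore fit a DRR driven almost entirely by function.

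**Step 3. Effect of dropping those who die**

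Assumptions not in the documents: log-normal slopes with coefficient of variation (CV) 0.5–0.8, and death hazard proportional to slope^g with g from 0.5 to 2, scaled to 5% control mortality. There were 4 million simulated participants per arm. The survivors-only ratio of mean slopes was combined with the mortality log-ratio using the Step 2 weights.

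| Scenario | CV, g | Function ratio, survivors only | Combined DRR | Probability of success |
|---|---|---|---|---|
| 30% slowing of both | 0.5, 0.5 | 0.701 | 0.701 | 0.839 |
| | 0.5, 2 | 0.705 | 0.705 | 0.828 |
| | 0.8, 1 | 0.707 | 0.706 | 0.825 |
| | 0.8, 2 | 0.713 | 0.712 | 0.806 |
| Full null | all six combinations | 1.00 | 1.00 | 0.025 |
| No functional effect, death hazard doubled | 0.5, 0.5 | 0.994 | 1.026 | 0.015 |
| | 0.8, 2 | 0.953 | 0.985 | 0.033 |

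The power loss is 0.843 − 0.839 = 0.4 points at the mild end and 0.843 − 0.806 = 3.7 points at the strong end.

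The harm rows keep mortality information at 3.1, its value under benefit. On that basis the combined ratio without any exclusion would be exp(3.1 × ln 2/69.2) = 1.03. Doubled mortality brings more deaths, about 22–23 (6.75 + 165 × 0.090 to 0.097), and information of 5.3–5.6. Recomputed with those values, the combined ratio is about 1.01–1.05, against 1.05–1.06 with no exclusion, and the probability of success is at most 0.022. Either way, the offset is partial and depends on the assumed slope–hazard link.

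**The case against.** **The wording may be shorthand.** The bullet may have meant only that scores after the event are not used, since visits can continue after a death equivalent. SAP 6.3 leaves model details to the MPRDR, which is not among the documents. RSA 9.1 and SAP Appendix 1, 1.0 list just two differences from the MPRDR, and discarding pre-event scores is not one of them. This stands as a possibility, so it cannot be said that the sponsor intends to drop them. It does not remove the point: the precedence table in SAP Section 1 ranks the R-SAP above the MPRDR for the primary analysis, so an analyst following the governing text would drop them.

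**The effect is small and may already be counted.** Table 3.2.1 shows a mean estimate of 0.70 under 30% slowing, with no visible attenuation. At two decimals that fits the mild cases above but not the strongest. The documents do not say whether those simulations applied the rule or linked slope to death. This stands: the power loss is conditional. The slope-ratio calculation also ignores baseline covariates, which may absorb some of the selection.

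**Other analyses cover it.** The repeated-measures and random-slopes models retain pre-death scores, time to death or death equivalent is analysed separately, and the Combined Assessment of Function and Survival (CAFS), which ranks deaths, is named a key sensitivity analysis. This limits the risk to interpretation. None of them re-estimates the DRR with pre-event scores. Further sensitivity analyses are imported from MPRDR Section 4.0, which cannot be checked here.

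**Stronger readings.** A reader might infer that the whole primary analysis is conditioned on survival, that type I error is inflated, or that a harmful drug could be declared a success. The documents support none of these. Deaths enter through the mortality component. The full null is unaffected, because both arms then lose the same kind of participant. In the harm case, the calculated probability of success stays between about 1% and 3%.

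**Conclusion.** The point holds for the function component and for the text as written. Read literally, the rule discards valid pre-event ALSFRS-R scores from about 13 to 15 of 300 participants in the component that supplies roughly 95% of the information on the DRR. It also puts the primary analysis out of step with its own supportive models.

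The size is modest. A true DRR of 0.70 becomes about 0.701–0.713 in the function component, with power between about 0.84 and 0.81 if the stated 0.843 did not already include the rule. With doubled mortality and no functional effect, the function component shows about 0.95–0.99. Mortality offsets this only partly, giving a combined 0.985–1.026 (about 1.01–1.05 with the larger number of deaths), and no false success is shown.

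All these figures rest on assumed slope spread and slope–hazard links and on a two-component approximation to the Bayesian model. The reading of the text does not. A change is worthwhile because it is cheap and removes a selection effect from the only gatekeeping test.

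**What to change.** Reword intercurrent event 1 in SAP 6.3 along these lines: *ALSFRS-R observations up to death or death equivalent are included in the function component; none after the event are used or imputed; the event enters the mortality component.* Adjust the closing clause of intercurrent event 2 to match, and reconcile both with the MPRDR model description. If only post-event scores were ever meant to be excluded, this is purely a correction of wording.

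If the sponsor keeps the participant-level exclusion to match the platform model, prespecify a sensitivity run of the primary model that includes pre-event scores. In either case, state which rule the Table 3.2.1 simulations used and whether they linked slope to death.

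The cost is SAP wording, data selection in the model code and, if the simulations used the other rule, a re-run. No new data are needed.
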